5. SUBJECT DISPOSITION

A listing of all Screen Failures (ie, subjects who were screened but not randomized) will be presented along with reasons for screen fail and details of any adverse events (AEs).

The number of subjects included in each analysis set (ie, Screened, Randomized, Safety, FAS and DRAS) will be summarized by treatment group, pooled doses and overall, except for the Screened Set, which will be summarized only overall.

The number and percentage of subjects who completed and prematurely discontinued during the Double-blind Evaluation Period will be presented for each treatment group, pooled doses and overall for the Safety Set. Reasons for premature discontinuation from the Double-blind Evaluation Period, as recorded on the end of study discontinuation page of the electronic case report form, will be summarized (number and percentage) by treatment group, pooled doses and overall for the Safety Set. The subjects who completed the study are those that completed the final scheduled visit at the end of the Double-blind Evaluation Period. When the interim analysis is conducted, for reporting purpose, an ongoing category will be added, and it will be reported by treatment, pooled doses and overall.

All subjects who prematurely discontinued during the Double-blind Evaluation Period will be listed by discontinuation reason for the Randomized Set.

The number of subjects randomized and completed will be tabulated by site. In addition, the duration of enrollment, in days, will be summarized for each site, and overall. Duration of enrollment will be calculated as (last date of contact for any subject at that site - the first date of informed consent for any subject at that site + 1).

Follow-up phone call information will be listed for the Safety Analysis Set.

6. PROTOCOL DEVIATIONS

Protocol deviations will be recorded by the site separately from the clinical database. The contract research organization will classify the protocol deviations per the agreed protocol deviation plan. The Shire study team will review the protocol deviations and their classification throughout the study and before treatment unblinding and database lock.

Decisions of the review will include accuracy of protocol deviation categorization.

For any criteria for protocol deviations that can be completely implemented by a computer program, the detailed algorithm will be agreed upon. Details of such algorithms will be included in the derived dataset specifications and finalized before treatment unblinding.

Confirmed protocol deviations will be documented in the Protocol Deviation tracker for the study. Protocol deviations will be summarized using the Randomized Set by category and site for each treatment group, pooled doses and overall. Protocol deviations will be listed for the Randomized Set.

7. DEMOGRAPHIC AND OTHER BASELINE CHARACTERISTICS

7.1 Demographic and Other Baseline Characteristics

Demographics and baseline characteristics will be examined to assess the comparability of the treatment groups at baseline, where baseline is defined as the last assessment prior to the first administration of the investigational product. The demographics and baseline data will be summarized by treatment group, pooled doses and overall for the Safety Analysis Set, FAS and DRAS. Listings will be provided as well.

Age will be calculated as the difference between date of birth (DOB) and date of informed consent (DINFC), truncated to months, using the following SAS function:

$$\text{Age} = \text{floor}((\text{intck}(\text{'month'}, \text{DOB}, \text{DINFC}) - (\text{day}(\text{DINFC}) < \text{day}(\text{DOB}))) / 12)$$

The Screening height and body weight will be used to calculate BMI using the following formula:

$$\text{BMI} = \frac{\text{Weight [kg]}}{(\text{Height [m]})^2}$$

The BMI should be rounded to 1 decimal place for reporting. BMI categories will be derived using the Centers for Disease Control and Prevention (CDC) BMI percentiles for children: Underweight – BMI less than the 5th percentile; Healthy Weight – BMI 5th percentile up to less than the 85th percentile; Overweight – BMI 85th percentile to less than the 95th percentile; Obese – BMI greater than or equal to the 95th percentile.

The following demographic characteristics will be summarized: age, sex, ethnicity, race, weight, height, BMI, and BMI category. In addition, other baseline characteristics to be summarized include the Peabody Picture Vocabulary Test standard score, Children's Global Assessment Scale scores, Clinical Global Impression – Severity of Illness (CGI-S), and ADHD subtypes. Continuous variables will be summarized by descriptive statistics including number of subjects, mean, SD, median, minimum, and maximum. Categorical variables will be summarized by the number of subjects in each category and the percentage of subjects out of the total in the respective analysis set.

All demographic and baseline characteristics will be listed for the Safety Analysis Set.

7.2 Medical History

Medical history is collected at the Screening Visit (Visit -1). Prior and ongoing psychiatric evaluation will be established with the Screening Visit (Visit -1) interview using the Kiddie-Schedule for Affective Disorders and Schizophrenia for School-age Children-Present and Lifetime Version-Diagnostic Interview (K-SADS-PL). Both of the assessment results will be listed for the Safety Analysis Set.

8. EXTENT OF EXPOSURE AND TREATMENT COMPLIANCE

8.1 Exposure to Investigational Product

Exposure to double-blind investigational product for the Safety Analysis Set will be summarized by treatment, pooled doses. The following statistics will be calculated for the Fixed-dose Titration Period, the Dose Maintenance Period, and the whole Double-blind Evaluation Period for the investigational product:

- Total days of dosing: sum of the days of dosing for each period. Within each period, it is defined as (date of last dose - date of first dose + 1)
- Average daily dose (mg/day) for SPD489: the total dose/total days of dosing
- Maximum dose for SHP489: the highest dose level received

An appropriate statistical summary will be applied to present for each of the above statistical quantity for each of the study period respectively. In addition, person-time (overall total exposure in days) will be derived. It is calculated as total number of days in which the investigational product was taken for each subject and then sum over all subjects for the whole duration of the study.

Dosing information will be listed.

If a subject is lost to follow-up without returning the leftover investigational product and without providing subsequent safety information, then the subject's dose information will be treated as missing. In particular, for the subjects lost to follow up after the Baseline visit (Visit 0), we will not assume any ingestion of the investigational product unless there is a post-baseline safety assessment. Subjects that do not return the investigational product but return to the site for a following visit will have zero capsule returned entered into the database. In this case, it will be assumed for analysis purposes that all capsules were ingested.

8.2 Measurement of Treatment Compliance

Investigational product dosing compliance, during the Dose Optimization Period, the Dose Maintenance Period, and the whole Double-blind Evaluation Period, respectively, is defined as the total number of capsules taken by a subject during that period divided by the number of capsules expected to be taken during the same period multiplied by 100, that is (number of capsules actually taken \times 100 / number of capsules expected to be taken). The number of capsules taken is calculated by the number of capsules dispensed minus the number of capsules returned. If a bottle is not returned, the number of capsules returned for that bottle will be imputed to 0. The number of capsules expected to be taken is calculated as the number of days the subject is in the particular period multiplied by the number of capsules to be taken per day during that period. If the number of capsules taken or returned is missing, then the compliance will be missing.

For each study period, the compliance data will be reported using number of subjects, mean, SD, median, minimum, and maximum for the Safety Analysis Set by treatment group and pooled

doses. Furthermore, the compliance data will be categorized as <80%, 80-120%, or >120%, and it will be presented using subject counts and percentages for the Safety Analysis Set by treatment group and pooled doses.

Treatment compliance data will also be listed for all subjects in the Safety Analysis Set.

9. PRIOR AND CONCOMITANT MEDICATION

The most updated available version of the World Health Organization drug dictionary will be used to classify prior and concomitant medications by therapeutic class.

Prior medication is defined as any medication with a start date prior to the date of the first dose of investigational product.

Concomitant medication is defined as any medication with a start date prior to the date of the first dose of investigational product and continuing after the first dose of investigational product or with a start date between the dates of the first and last doses of investigational product, inclusive. Any medication with a start date after the date of the last dose of investigational product will not be considered a concomitant medication.

Both prior and concomitant medication usage (including ADHD medication) will be summarized by the number and proportion of subjects within each preferred term for the Safety Analysis Set by treatment group and pooled doses. Medications can be counted both as prior and concomitant medication. Multiple medication usage by a subject in the same category will be counted only once. Both prior and concomitant ADHD medication usage (based on indication), excluding investigational product, will also be summarized by the number and proportion of subjects within each preferred term for the Safety Analysis Set by treatment group and pooled doses.

All prior and concomitant medication will be listed for the Safety Analysis Set. Separate listings will also be provided for prior and concomitant ADHD medication and prior and concomitant ADHD behavioral therapy.

10. EFFICACY ANALYSES

The primary and key secondary analyses, including their sensitivity analyses, will be based on the FAS and will be conducted on either the interim analysis dataset, which is defined in Section 2.6, or all cumulative data up to study completion, whenever it is appropriate. Specifically, these analyses will compare placebo and pooled SPD489 10, 20, 30 mg dose strengths together, excluding the 5 mg arm. For primary and key secondary endpoints, statistical tests are planned to control the study-wise type I error at the 2-sided 5% level, as described in Section 2.6. All other statistical tests will be 2-sided hypothesis tests performed at the 5% level of significance, with no adjustment for multiplicity. All confidence intervals (CIs) will be 2-sided 95% CIs, unless stated otherwise. Additionally, the dose response relationship evaluations will be performed over the DRAS and using appropriate datasets. For this analysis, all randomized investigational product groups, which include 0 (placebo), 5, 10, 20, 30 mg (SPD489) dose strengths will be used.

Baseline for all efficacy analyses is defined as the last valid value for the efficacy assessment prior to the first dose of investigational product. An efficacy measurement that is assessed more than 3 days after the date of the last dose of investigational product will not be included for analysis.

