## 9.7 Study Population

The **Screened Set** will consist of all subjects who have signed an informed consent.

The **Randomized Set** will consist of all subjects in the Screened Set for whom a randomization number has been assigned.

The **Safety Analysis Set** will consist of all subjects in the Randomized Set who have taken at least 1 dose of investigational product.

The **Full Analysis Set** (FAS) will consist of all subjects in the Safety Analysis Set who have at least 1 post baseline ADHD-RS-IV Preschool Version Total Score assessment, where baseline is defined as the last valid assessment prior to taking the first dose of investigational product.

The **Dose Response Analysis Set** (DRAS) will consist of all subjects in the Safety Analysis Set who have at least 1 valid primary efficacy measurement (ADHD-RS- IV Preschool Version Total Score) on the randomized target dose level of the investigational product.

The above analysis sets are similarly defined for both the interim and the complete study analyses.

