## 9.8 Efficacy Analyses

The primary and key secondary analyses, including sensitivity analyses, will be based on the FAS and will be conducted on either the interim analysis dataset or all cumulative data up to study completion, whenever it is appropriate. Specifically, these analyses will compare between placebo and pooled SPD489 10, 20, 30 mg dose strengths together, excluding the 5 mg arm. For primary and key secondary endpoints, statistical tests are planned to control the study-wide type I error at the 2-sided 5% level, as described in Section 9.5. All other statistical tests will be 2-sided hypothesis tests performed at the 5% level of significance, with no adjustment for multiplicity. All confidence intervals will be 2-sided 95% confidence intervals, unless stated otherwise. In addition, the dose response relationship evaluations will be performed over the DRAS and using appropriate datasets. For this case, all randomized investigational product groups, which include 0 (placebo), 5, 10, 20, 30 mg (SPD489) doses will be used.

Rules for missing data handling will be described in the SAP.

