4.4 Full Analysis Set

The Full Analysis Set (FAS) will consist of all subjects in the Safety Analysis Set who have at least 1 post-dose ADHD-RS-IV-Preschool Version Total Score assessment.

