10.2 Sensitivity Analyses for the Primary Efficacy – Missing Not at Random

The primary efficacy analysis (MMRM) relies on the assumption that the missing data mechanism follows the missing at random (MAR) scenario. In this case, it is assumed that the reason for data being missing may depend on observed data, but not on the unobserved missing data. The likelihood-based MMRM analysis is an appropriate method for the statistical analysis under MAR assumption.

The following 2 sensitivity analysis models, which are within the pattern-mixture model framework, will be used to examine the robustness of the primary efficacy analysis results for the missing not at random (MNAR) mechanisms. Under MNAR, it is assumed that the reason for data being missing is related to the unobserved missing data.

Model 1: Placebo Multiple Imputation

Rationale: The imputations are based on the distribution of placebo group responses over time. The underlying assumption is that the missing data for a subject on the active treatment follow the distribution of the placebo responses, i.e., the mean values and intra-subject correlations based on the placebo responses will be applied.

The model is implemented in 3 steps: 1) imputations, 2) analysis of complete data sets, and 3) inference. Sample SAS codes are provided in [Appendix 2](#).

Step 1: Imputations

A total of 200 sets of posterior mean and co-variance estimates are extracted from the SAS MI procedure using the available non-missing placebo data. One hundred of the posterior sets will be applied to the pooled active treatment group, while the other 100 will be applied to the placebo group. One set of imputations for all missing values will be generated based on each variation of posterior estimates. All 100 datasets for imputations within a treatment group will be ordered from 1 to 100 and combined between pooled active treatment group and placebo, for a total of 100 completely imputed datasets.

Step 2: Analysis of Complete Datasets

The primary efficacy endpoint will be analyzed for each of the 100 complete datasets with imputed data using an analysis of covariance with treatment group as factors and the baseline value as a covariate.

Step 3: Inference

The LS mean difference estimates will be averaged, and the associated SEs will be summarized based on within-imputation and between-imputation variance using the SAS MIANALYZE procedure to yield a final estimate with associated 95% CI and p-value.

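### Both missing-not-at-random sensitivity models are confined to the FAS, so a randomised child with no post-dose ADHD-RS rating is left out of the analyses meant to test dropout

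*SAP*

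**What the plan says.** Protocol 9.8 sets the population: "The primary and key secondary analyses, including sensitivity analyses, will be based on the FAS". SAP section 10 repeats this for the same analyses, "including their sensitivity analyses, will be based on the FAS", and SAP section 17 lists no change from the protocol.

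Under SAP 4.4 the FAS consists of dosed children "who have at least 1 post-dose ADHD-RS-IV-Preschool Version Total Score assessment". Protocol 9.7 likewise asks for "at least 1 post baseline ADHD-RS-IV Preschool Version Total Score assessment".

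SAP 10.2 gives two models, placebo multiple imputation (Model 1) and multiple imputation with a penalty for dropouts (Model 2), which "will be used to examine the robustness of the primary efficacy analysis results for the missing not at random (MNAR) mechanisms". SAP 10.3 reuses both for CGI-I. Neither section names a wider population, and no planned efficacy analysis uses the Randomized Set or the Safety Analysis Set.

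Three other provisions decide who is affected:

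- Protocol 4.4, 7.1.2.3 and 7.2 ask for the Visit 6/ET evaluations when a child discontinues, and the Protocol's Table 1 includes the ADHD-RS at that visit.
- SAP section 10 leaves out efficacy ratings made more than 3 days after the last dose.
- SAP 8.1 does not assume that a child lost after Visit 0 took any product unless there is a post-baseline safety assessment.

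**The concern.** Whether a child has a post-dose rating is settled after randomisation, and treatment can influence it: Protocol 6.2.3 has children who cannot tolerate the product discontinued. A primary analysis on such a set is a choice that can be defended. The two models, however, exist to ask what happens if dropouts fare worse than the missing-at-random analysis assumes. Confined to the FAS, they leave out the dropouts with the least data, so they cannot show whether that exclusion matters. A statement that the result is robust to dropout would cover only dropouts who gave at least one post-dose rating.

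The data do not force this. Inclusion criterion 5 requires a Visit 0 ADHD-RS score, and the sample imputation code in SAP Appendix 2 already starts from the baseline value.

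**Working it through.** **Inputs.** From SAP 2.5: difference 8.4, SD 14, dropout 20%, 195 randomised in the ratio 5:5:5:5:6, and 156 completers (30 per active arm, 36 on placebo). The share of children with no post-dose rating, q, is not given. It is assumed here to be 0%, 3%, 5% or 10%.

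**The plan's own figures.**

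- Randomised: 156 / 0.8 = 195, as stated.
- Power for 90 v 36: 8.4 / (14 × √(1/36 + 1/90)) = 3.04, giving 86.1% by the normal formula and 85.5% by the noncentral t, against 85% stated.

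The design figures reproduce. They are not in dispute, and power plays no further part.

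**Children in the primary comparison.**

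- Placebo, 10, 20 and 30 mg: 195 × 21/26 = 157.5 randomised (112.5 active, 45 placebo).
- Completers: 90 + 36 = 126.
- Dropouts: 157.5 − 126 = 31.5.

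**Simplified Model 1.** Assume 20% dropout and the same q in both arms, an effect of 8.4 in completers, and no drug effect in any imputed active child. The estimate is then 8.4 times the share of analysed active children who completed.

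- All randomised: 8.4 × 0.80 = 6.72.
- FAS only: 8.4 × 0.80 / (1 − q) = 6.72 / (1 − q).

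| q | Children removed (157.5 × q) | FAS Model 1 | All-randomised Model 1 | Gap |
|---|---|---|---|---|
| 0% | 0 | 6.72 | 6.72 | 0 |
| 3% | 4.7 | 6.72 / 0.97 = 6.93 | 6.72 | 0.21 |
| 5% | 7.9 | 6.72 / 0.95 = 7.07 | 6.72 | 0.35 |
| 10% | 15.8 | 6.72 / 0.90 = 7.47 | 6.72 | 0.75 |

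The last row supposes that half of the planned 20% dropout happens without any post-dose rating, early termination included. It is an upper illustration and not an expectation.

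The zero-effect assumption is a simplification for rated dropouts, because the actual model also uses their earlier ratings. For a child with only a baseline score it is close to what Model 1 does.

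**Model 2.** The sample code adds the penalty to missing Visit 6 values without regard to arm. Each arm's mean shifts by the penalty times its imputed share, so equal shares cancel in the difference. The exclusion therefore matters for Model 2 mainly if unrated losses differ between arms. That is why Model 1 comes first in the fix.

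**The case against.** **Early-termination ratings.** A reader might infer that early drug-related losses cannot lower the estimate in any planned analysis. The documents do not support that. A child who stops in week 1 and attends the ET visit within 3 days of the last dose has a usable post-dose rating and enters the FAS; the missing Week 6 value is then placebo-imputed or penalised. This stands, and it narrows the point to children with no ET rating. Children whose ET rating comes too late to be analysed may also be affected, since the SAP does not say whether such a rating still counts for FAS entry.

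**The estimand.** Protocol 9.8.1 and SAP 10.1 define the effect for children in the FAS, so holding the population fixed isolates the missing-at-random assumption. This also stands: the documents agree with each other, and the FAS-based runs should stay. It does not remove the gap, because a check inside the FAS cannot test the selection into it.

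**Size and power.** A reader might set 8.4 against 8.4 × (1 − q), or infer a loss of power. The first treats unrated children as the only dropouts, whereas Model 1 also placebo-imputes the rated ones. The second would pair the completer numbers, 90 v 36, with an analysis of everyone randomised to those arms, and power is not the criterion for a sensitivity analysis.

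**Never-dosed children.** Losses before dosing cannot be drug-related in a blinded trial, and the SAP's baseline rule refers to the first dose. Both are true, and the fix needs a baseline convention. The Safety Analysis Set alone may not suffice, however: under SAP 8.1 a child lost straight after Visit 0 is treated as not having taken product and could fall outside that set too.

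**Visibility.** SAP section 5 tabulates the size of each analysis set and the reasons for discontinuation by group. An imbalance would be seen, but its effect on the estimate would not be measured.

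**Conclusion.** The point holds in a limited form. Both models omit every randomised child without a post-dose ADHD-RS rating, and no other planned efficacy analysis brings these children back. How many there will be is unknown and may be few, because early-termination ratings are requested.

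Under the stated assumptions (20% dropout and equal unrated shares in both arms, and no drug effect in imputed active children), the FAS version of Model 1 is about 0.2 to 0.75 points more favourable than the all-randomised version for unrated shares of 3% to 10%. It is identical if there are none. The primary MMRM, the alpha plan and the sample size are untouched. This is a cheap improvement to the sensitivity plan, and the documents do not show an error in the primary analysis.

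**What to change.** Keep the FAS for the primary MMRM and for the sensitivity analyses already planned on it. Add to SAP sections 10 and 10.2 that:

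- Model 1, and preferably Model 2, will also be run on all randomised children in the placebo, 10, 20 and 30 mg arms;
- where no post-dose rating exists, imputation starts from the Visit 0 score;
- for never-dosed children, the Visit 0 score serves as baseline.

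The cost is a short addition to the text, a wider input dataset and one further run per model. The downside is a little more analysis work and a slightly less favourable sensitivity estimate if some children are unrated.
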